### **8.1.5 Clinical Laboratory Data**

Clinical laboratory tests will be summarized at each visit by treatment arm. The baseline value will be the last non-missing measurement prior to the initial dose of study drug. Mean changes from baseline to each post-baseline visit, including the Final Treatment Visit, will be summarized descriptively for each treatment arm.

In addition, the number and percentage of subjects with post-baseline laboratory values showing increase in CTCAE toxicity grade during treatment will be summarized by treatment arm for the Main study and overall for the Retreatment sub-study.

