**Safety:**

All subjects who receive at least one dose of study drugs will be included in the safety analyses. Adverse events will be coded using the Medical Dictionary for Regulatory Activities (MedDRA) and will be summarized by subject's final treatment arm assignment. Safety summaries will be provided by treatment group of the Main study and overall for the Retreatment sub-study. The number and percentage of subjects with treatment-emergent adverse events (i.e., any event that begins or worsens in severity after initiation of study drug) will be tabulated by primary System Organ Class (SOC). The tabulation of the number of subjects with treatment-emergent adverse events also will be provided by grade and relationship to study drug. Change from baseline in laboratory tests to each time point of collection will be summarized by subject's final treatment arm assignment. Laboratory values that show an increase in CTCAE grade will be summarized.

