**Table 3. Adverse Events Reported for  $\geq 5.0\%$  of Subjects (Phase 2 and 3 Analysis Set)**

	Phase 2 and 3 Analysis Set a (N = 2,265)	
	All Adverse Events	DAA-Related Adverse Events b
Any AE	1,529 (67.5)	929 (41.0)
An AE Grade $\geq 3$	65 (2.9)	4 (0.2)
Any SAE	48 (2.1)	1 (< 0.1)
Discontinuation of study drug due to any AE	8 (0.4)	3 (0.1)
All deaths c	6 (0.3)	0
Preferred Termd		
Headache	410 (18.1)	298 (13.2)
Fatigue	330 (14.6)	259 (11.4)
Nausea	208 (9.2)	172 (7.6)
Diarrhea	146 (6.4)	86 (3.8)

AE = adverse event; DAA = direct-acting antiviral agent; GLE = glecaprevir; PIB = pibrentasvir; SAE = serious adverse event

a. Excludes Study M15-462.

b. DAAs = GLE, PIB, or GLE/PIB.

c. Includes non-treatment-emergent deaths. One additional death occurred in Study M15-462.

d. DAA-related AEs reported for  $\geq 5.0\%$  of subjects in the Phase 2 and 3 Analysis Set.

Cross reference: AbbVie, data on file.

Adverse events in subjects without cirrhosis (n = 1,977) were similar in type, frequency, and severity compared with subjects with cirrhosis (n = 288). The safety profile in subjects with HCV/HIV-1 co-infection (n = 33) was similar to that in HCV mono-infected subjects. Overall, the safety profile of G/P in the elderly population ( $\geq 65$  years old, n = 328) was comparable to the safety profile in the non-elderly population (n = 2,041).

The frequency and severity of hepatic-related AEs as well as liver chemistry abnormalities evaluating potential hepatotoxicity were low across the Phase 2 and 3 studies. Liver-related safety results indicated that:

- Four subjects had post-nadir Grade 3 ALT abnormalities or Grade 2 ALT with total bilirubin  $\geq 2 \times$  ULN. None of these subjects prematurely discontinued study drug due to an ALT or bilirubin increase.
- ALT abnormalities in 3 of these 4 subjects were not clinically significant

- One subject experienced concurrent ALT  $> 3 \times$  ULN (increased from nadir grade) and total bilirubin  $\geq 2 \times$  ULN in the context of multiple gallstones and was not considered to have drug-induced liver injury
- Based on exposure-response analyses, no exposure-dependent ALT increases were observed in subjects with ALT abnormalities
- Grade 3 increases in bilirubin were infrequent (0.4%) and without bilirubin-related AEs; none were associated with liver disease progression

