### **5.2.2                   Exclusion Criteria**

1. Female subject who is pregnant, breastfeeding, or is considering becoming pregnant during the study or for 30 days after the last dose if randomized to G/P or 6 months after the last dose if randomized to RBV (or as directed per the local RBV label).

Male subject whose partner is pregnant or planning to become pregnant during the study or for 30 days after the last dose if randomized to G/P or 7 months after the last dose if randomized to RBV (or as directed per the local RBV label).

2. HCV genotype performed during screening indicating infection with any non-GT1 HCV genotype (applicable during screening for Main Study only).
3. Requirement for and inability to safely discontinue the medications or supplements listed in **Table 4** at least 2 weeks or 10 half-lives (whichever is longer) prior to the first dose of any study drug.

4. Clinically significant abnormalities or co-morbidities, or recent (within 6 months prior to study drug administration) alcohol or drug abuse that make the subject an unsuitable candidate for this study in the opinion of the investigator.
5. Positive test result at Screening for hepatitis B co-infection (HBsAg positive or Hep B Core Ab -Total positive with detectable HBV DNA) or anti-human immunodeficiency virus antibody (HIV Ab) in a patient without known history of HIV+ and stable HART therapy (applicable during screening for Main Study only).
6. Screening laboratory analyses showing any of the following abnormal laboratory results:
  - Total bilirubin  $\geq 3.0$  mg/dL.
  - Albumin  $< 2.8$  g/dL.
  - Hemoglobin  $< 11$  g/dL for women;  $< 12$  g/dL for men, applicable only to subjects receiving RBV
7. Prior therapy with a HCV Protease Inhibitor at any time (applicable during screening for Main Study only).
8. Receipt of any investigational product within a time period equal to 10 half-lives of the product, if known, or a minimum of 6 weeks (whichever is longer) to study drug administration.
9. Consideration by the investigator, for any reason, that the subject is an unsuitable candidate to receive G/P or, if cirrhotic, RBV (applicable to Main Study only, see exclusion #12 for considerations for Retreatment sub-study).
10. History of severe, life-threatening or other significant sensitivity to any excipients of the study drugs.
11. Subjects who cannot participate in study per local law.

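### Section 8.1.5 names no reference for its CTCAE grade-increase count; read as from baseline, the table omits ALT or AST rises from an on-treatment nadir that stop at or below the baseline grade, whereas Section 3.1.4 reports ALT post-nadir

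*Protocol*

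**What the plan says.** Section 8.1.5 gives three things for laboratory data.

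- A definition of baseline: "The baseline value will be the last non-missing measurement prior to the initial dose of study drug".
- A summary of central tendency: "Mean changes from baseline to each post-baseline visit, including the Final Treatment Visit, will be summarized descriptively for each treatment arm".
- A categorical count, in a separate paragraph: "the number and percentage of subjects with post-baseline laboratory values showing increase in CTCAE toxicity grade during treatment will be summarized by treatment arm" in the Main study, and overall in the Retreatment sub-study.

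The Synopsis (Safety) has a shorter form of the count: "Laboratory values that show an increase in CTCAE grade will be summarized". Neither place names the value from which the increase is measured, and neither mentions a nadir. In the planned procedures and analyses, nadir appears only for HCV RNA (Sections 5.4.1.1 and 8.1.2.2).

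Section 3.1.4, on the earlier experience with the same regimen, reports ALT differently. It says "Four subjects had post-nadir Grade 3 ALT abnormalities or Grade 2 ALT with total bilirubin" at least twice ULN. It also describes one subject with ALT above 3x ULN, qualified as "increased from nadir grade", and concurrent total bilirubin of at least 2x ULN.

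**The concern.** Safety and tolerability form the third primary objective (Section 4.1), and Section 3.1.4 gives liver safety particular attention for this protease-inhibitor regimen. The grade-increase count is the one laboratory summary in Section 8.1.5 that works subject by subject and by toxicity grade.

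The choice of reference matters when a subject enters with a raised enzyme that falls on treatment. If the enzyme later rises to the entry grade or to a grade below it, a count from baseline records no worsening, while a count from nadir records an increase. Nothing at entry prevents this pattern. The exclusion headed "Screening laboratory analyses showing any of the following abnormal laboratory results" (Section 5.2.2, criterion 6) lists bilirubin, albumin and haemoglobin, with no ALT or AST limit.

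At stake are the sensitivity of a descriptive liver-safety table and whether it can be set beside the post-nadir ALT results in Section 3.1.4.

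**Working it through.** The protocol states no figure on this point, so there is none to reproduce. The check is one of logic and needs no CTCAE cut-offs.

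**Set-up.** Let b be the baseline grade, n the lowest grade up to the later visit (n <= b, baseline included), and p a later on-treatment grade that has risen from it (p > n). Grades run from 0 to 4. A count from baseline records the subject if p > b. A count from nadir records the subject if p > n.

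**Enumeration.** For a given b, the possible rises from nadir number the sum of (4 - n) over n = 0 to b. Those missed by the baseline count have n < p <= b, which gives b(b + 1)/2 patterns.

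| Baseline grade b | Possible rises from nadir | Missed if counted from baseline |
|---|---|---|
| 0 | 4 | 0 |
| 1 | 4 + 3 = 7 | 1 x 2/2 = 1 |
| 2 | 4 + 3 + 2 = 9 | 2 x 3/2 = 3 |
| 3 | 4 + 3 + 2 + 1 = 10 | 3 x 4/2 = 6 |
| 4 | 4 + 3 + 2 + 1 + 0 = 10 | 4 x 5/2 = 10 |

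These are counts of possible patterns, not expected frequencies of patients.

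**Examples.** The path 2, 0, 2 gives 2 - 2 = 0 from baseline (not counted) and 2 - 0 = 2 from nadir (counted). The path 2, 0, 3 gives 3 - 2 = 1 from baseline and 3 - 0 = 3 from nadir, so both rules count it. A subject entering at grade 0 is never affected.

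**Against the categories in Section 3.1.4.** A post-nadir Grade 3 ALT (p = 3) is missed by the baseline count only if b >= 3. The ALT part of a Grade 2 ALT with raised bilirubin (p = 2) is missed only if b >= 2.

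**Does mean change recover the case?** No. It is a group average at each visit, and a subject who has returned exactly to the baseline value contributes zero to it.

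**Do adverse events recover it?** In part. The text after Table 8 requires an adverse event when a value leads to discontinuation, a ribavirin dose modification or treatment. Arms A, B and D have no planned ribavirin, and Section 5.5.1 allows no G/P dose adjustment. Section 6.1.2 grades severity by the treatment given, so an untreated enzyme rise, if recorded, is coded mild whatever its laboratory grade.

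**The case against.** The strongest reply is that the protocol does not state the rule being criticised. The grade sentence names no reference, stands in a separate paragraph from the baseline definition, and could be read as a rise from any earlier value. Section 8.1 leaves further analysis detail to the SAP, which was not available for this review and may settle the matter. This stands to the extent that the defect is an unstated reference, not a demonstrated decision to reject nadir. It does not remove the point: baseline is the only laboratory reference the protocol defines, and its own account of the regimen uses another for ALT.

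A reader might infer that such rises are never captured anywhere. The documents do not support that. Rises above the baseline grade are counted under either reading, values acted upon become adverse events, an abnormal laboratory finding can itself be an adverse event (Section 6.1.1.1), and investigators sign the central reports for clinical significance (Section 6.1.7).

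A reader might also infer that Section 3.1.4 used nadir because a baseline comparison would miss cases. That section gives no reason. Nor does the protocol say that ALT starts raised and falls on therapy. The post-nadir wording and the absence of an entry limit only make this plausible.

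On size, the reply is that such events are rare. Four subjects met the Section 3.1.4 criteria. If the same rate applied to 225 subjects, 4/2,265 x 225 = 0.40, or 4/2,369 x 225 = 0.38, would be expected, and a baseline count would miss only some of them. This is a fair guide to the rarity of the more marked events. It does not estimate how many lower-grade rises from nadir the table would omit.

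**Conclusion.** The point holds as a minor one. Section 8.1.5 leaves the reference for grade increase unnamed. On the natural reading, its table does not count an ALT or AST rise from an on-treatment nadir that ends at or below the baseline grade, and its basis differs from that of Section 3.1.4.

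This rests on two assumptions: that baseline is the intended reference, and that some subjects enter with raised ALT or AST that then falls. The number affected cannot be computed, since the protocol gives no distribution of entry grades. The effect is confined to a descriptive safety table. SVR12 and the other efficacy analyses are untouched.

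**What to change.** In Section 8.1.5, and in the matching Synopsis sentence:

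1. State that an increase in CTCAE grade is measured from baseline, as the general rule for laboratory tests.
2. For ALT and AST, add the number and percentage of subjects with a post-nadir grade increase. Define nadir as the lowest grade from baseline up to the visit before the one assessed. Including baseline ensures that every increase from baseline is also counted post-nadir.
3. Add a listing of subjects with post-nadir ALT >3x ULN together with total bilirubin >=2x ULN, in line with Section 3.1.4.

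The cost is one table and one listing. Table 5 already schedules central chemistry on Day 1 and at every treatment visit, so no new samples are needed. The drawback is that the post-nadir count will include some low-grade fluctuation. Showing it beside the baseline-referenced count, by grade reached, lets the reader judge that.

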### **Definition of Terms**

Study Drug	Glecaprevir (ABT-493), pibrentasvir (ABT-530), Ribavirin (RBV), *Sofosbuvir (GS-7977)
Study Day 1	First day of study drug dosing
Treatment Period	Day 1 through last dose of study drug
Post-Treatment Period	Day after the last dose of study drug through Post-Treatment Week 12 or Post-Treatment Discontinuation

Note: Differentiation between terms within the Main Study and Re-Treatment Substudy will be made with the use of headers throughout the protocol

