### **5.1.5 Post-Treatment Period**

All subjects who received at least one dose of study drug will be monitored in the Post-Treatment Period for safety, HCV RNA, and the emergence and persistence of resistance-associated viral substitutions for an additional 12 weeks following the last dose of study drug.

All original clinic notes, telephone notes, locally available safety labs/evaluations and/or diagnostic tests or health screenings collected during the post HCV treatment period will be submitted for chart data abstraction to identify and abstract adverse events, vital signs, physical examinations, concomitant medications, HCV RNA, HCV resistance, and clinical laboratory tests that were collected as part of standard of care practice. Sites will also perform a verification of the medical records to review for new clinical interactions that may have occurred from end of treatment through 12 weeks post treatment which may coincide with applicable central laboratory collection visits. All applicable clinical records for adverse event and serious adverse event monitoring in the post treatment period will be submitted for chart data abstraction.

The Post-Treatment Period will begin the day following the last dose of study drug treatment. Study visits during the Post-Treatment Period are detailed in **Table 6** of Section 5.3.1.

Subjects who prematurely discontinue the Post-Treatment Period should return to the site for a Post-Treatment Discontinuation Visit as outlined in **Table 6** and will be followed for all post-treatment safety, HCV RNA, and resistance-associated substitutions according to the post treatment period schedule.

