**Table 5. Study Activities – Treatment Period for Main study and Retreatment sub-study**

*Subjects assigned to a 12-week treatment duration will not complete the Wk16 EOT visit. Any patient eligible to receive treatment in the Retreatment sub-study will be assessed as noted for screening and according to ALL on-treatment evaluations outlined in the activities table.*

Activity	Screening	Day 1 a	Wk 4	Wk 8	Wk 12 or EOT	Wk 16 EOT	Premature D/C b
STANDARD OF CARE and documented in Medical Record							
Demographics & Medical History (including history of hepatic decompensation and Prior HCV Therapy)	X						
Physical Exam & Child-Pugh Score	X						
Vital Signs, Weight, Height d	X						
Cirrhosis Determination (per Section 5.2.3)	X						
Concomitant Medication Assessment	X n						
Adverse Event/Serious Adverse Event Assessment e	X m						
HCC Screening documentation as applicable to subjects with cirrhosis (within 6 months of screening) f	X						
For HIV co-infected subjects, CD4+ & HIV RNA results obtained locally (per Inclusion 9)	X p						

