**Table 6. Study Activities – Post-Treatment (PT) Period for Main study and Retreatment sub-study**

Activity	PT Wk 4	PT Wk 12
Physical Exam & Child-Pugh Score	As available for abstraction per SOC in the submitted redacted medical records	
Vital Signs, Weight	As available for abstraction per SOC in the submitted redacted medical records	
Concomitant Medication Assessment a	As available for abstraction per SOC in the submitted redacted medical records	
Adverse Event/Serious Adverse Event Assessment b	As available for abstraction per SOC in the submitted redacted medical records	
Hematology/Chemistry/PT/INR c	X	
HCV RNA Samples c	X	X
Pregnancy Test (urine [u]) for WOCBP only e	X (u)	X(u) d
HCV Resistance Sample c	X	X
Archive Plasma Sample c	X	X
Upload signed central lab reports evaluating clinical significance of abnormal results	X	X
Medical Records & Blood sample collection Verification Worksheet and Records Submission	X	X
For HIV co-infected subjects, CD4+ & HIV RNA results obtained locally	As available for abstraction per SOC in the submitted redacted medical records	

Wk = Week; PT D/C = Post-Treatment Discontinuation

- a Only medications taken for SAEs and for treatment of HCV will be collected after 30 days post-dosing.
- b Non-serious AEs will be collected until 30 days post dosing. All SAEs will be collected through PT WK 12. (see Section 6.1.4).
- c Collected for central laboratory processing
- d Required for WOCBP randomized to RBV arm only, or subjects of Re-treatment study who receive RBV as part of the retreatment regimen
- e If the urine pregnancy result is positive, site must confirm immediately with a serum test collected through the central laboratory

Note: Day 1 of the Post-Treatment Period will be defined as the day after the last dose of study drug.

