### **5.4 Removal of Subjects from Therapy or Treatment Duration Assessment**

#### **5.4.1 Discontinuation of Individual Subjects**

Each subject has the right to withdraw from the Main study or Re-treatment substudy at any time. In addition, the investigator may discontinue a subject from the Main study or Re-treatment substudy at any time if the investigator considers it necessary for any reason, including the occurrence of an adverse event or noncompliance with the protocol.

If, during the course of study drug administration, the subject prematurely discontinues, the procedures outlined for the applicable Premature D/C Visit should be completed as defined in **Table 5** and **Table 6**. Ideally this should occur on the day of study drug discontinuation, but no later than 2 days after their final dose of study drug and prior to the initiation of any other anti-HCV therapy. However, these procedures should not interfere with the initiation of any new treatments or therapeutic modalities that the investigator feels are necessary to treat the subject's condition. Following discontinuation of study drug, the subject will be treated in accordance with the investigator's best clinical judgment. The last dose of any study drug and reason for discontinuation will be recorded in the medical record and submitted for centralized abstraction. The subject should then begin the Post-Treatment Period where the subject will be monitored for 12 weeks for HCV RNA and the emergence and persistence of resistant viral variants.

If a subject is discontinued from study drugs or the Post-Treatment Period with an ongoing adverse event or an unresolved laboratory result that is significantly outside of the reference range, the investigator will attempt to provide follow-up until a satisfactory clinical resolution of the laboratory result or adverse event is achieved.

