#### **8.1.4 Adverse Events**

All subjects who receive at least one dose of study drug will be included in the safety analyses. Safety analyses will be conducted separately for the Main study and the Retreatment sub-study.

Adverse events will be coded using the Medical Dictionary for Regulatory Activities (MedDRA). The number and percentage of subjects with treatment-emergent adverse events (i.e., any event that begins or worsens in severity after initiation of study drug through 30 days post-study drug dosing) will be tabulated by primary MedDRA System Organ Class (SOC) and preferred term (PT) for each treatment arm. The tabulation of the number of subjects with treatment-emergent adverse events by severity grade and relationship to study drug also will be provided. Subjects reporting more than one adverse event for a given MedDRA preferred term will be counted only once for that term using the most severe grade for the severity grade table and the most related for the relationship to study drug table. Subjects reporting more than one type of event within a SOC will be

counted only once for that SOC. Selected adverse events will be summarized separately for the Re-treatment Substudy.

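### The CTCAE grade-increase table stops at the end of treatment, so the mandatory Post-Treatment Week 4 safety labs enter no CTCAE-graded subject count

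*Protocol*

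**What the plan says.** Section 8.1.5 plans three laboratory outputs: summaries at each visit, mean changes from baseline to each post-baseline visit, and a count of subjects by toxicity grade. For the last it says that "the number and percentage of subjects with post-baseline laboratory values showing increase in CTCAE toxicity grade during treatment will be summarized", by arm in the Main study and overall in the Retreatment sub-study. The Safety paragraph of the synopsis describes this output without a time limit: "Laboratory values that show an increase in CTCAE grade will be summarized".

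The Definition of Terms sets the Treatment Period as "Day 1 through last dose of study drug". Section 5.1.5 adds: "The Post-Treatment Period will begin the day following the last dose of study drug treatment". In Table 6 the row "Hematology/Chemistry/PT/INR" is marked at Post-Treatment Week 4 and left blank at Post-Treatment Week 12. Section 8.1.4 counts an adverse event as treatment-emergent if it begins or worsens "after initiation of study drug through 30 days post-study drug dosing".

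**The concern.** Safety and tolerability of G/P with or without RBV is the third primary objective (section 4.1). The grade-increase table is the only planned output that shows how many subjects had a laboratory value worsen on the CTCAE scale. If it closes at the last dose, a subject whose ALT or hemoglobin first worsens in grade at Post-Treatment Week 4 is not in it, although the sample is mandatory and centrally processed. The adverse-event and laboratory tables then cover different periods after dosing, with no reason given, and the synopsis and section 8.1.5 word the same output differently.

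**Working it through.** The plan states no figure to reproduce. The check places each rule on a scale of days after the last dose.

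| Item | Source | Days after last dose |
|---|---|---|
| Treatment Period ends | Definition of Terms | 0 |
| Post-Treatment Period begins | Section 5.1.5 | +1 |
| Premature D/C visit | Section 5.4.1 | 0 to +2 |
| Post-Treatment Week 4 labs | Table 6 | 4 × 7 = +28, nominal |
| Treatment-emergent adverse-event window ends | Section 8.1.4 | +30 |

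1. *Post-Treatment Week 4 against the grade table.* Day +28 is after day 0, so under the on-treatment limit these values do not enter.

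2. *Post-Treatment Week 4 against the adverse-event window.* Day +28 is before day +30, so at the nominal day the visit lies inside the period in which adverse events are counted.

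3. *How many scheduled draws are affected.* Day 1 samples are taken before the first dose and serve as baseline. Post-baseline safety draws in Arms A and C are Weeks 4, 8 and 12 plus Post-Treatment Week 4, so 1 of 4 is left out. In Arms B and D, and in the 16-week Retreatment sub-study, Week 16 is added, so 1 of 5 is left out.

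4. *Comparison between arms.* In Arms A and C, Post-Treatment Week 4 falls at nominal study week 12 + 4 = 16. Arms B and D have their end-of-treatment draw then. That draw counts in B and D; the draw at the same nominal week in A and C does not. Counted draws are 3 against 4 now, and would be 4 against 5 if Post-Treatment Week 4 were added. The imbalance shrinks in relative terms but remains.

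5. *Whether other outputs fill the gap.* The by-visit summaries and mean changes include Post-Treatment Week 4, but a mean does not show how many subjects changed grade. Adverse-event tables are by subject and by severity, but section 6.1.2 sets severity by the treatment given, RBV dose reduction or study drug discontinuation (plus transfusion for anemia), not by CTCAE grade. The text under Table 8 makes a laboratory value an adverse event only if it requires discontinuation, an RBV dose change or treatment. After the last dose, the first two seldom apply. Section 6.1.1.1 permits an abnormal laboratory finding to be an adverse event but does not require it. An untreated grade increase first seen at Post-Treatment Week 4 therefore enters no CTCAE-graded table and need not enter an adverse-event table.

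6. *Whether a plain 30-day limit would do.* The protocol gives no visit window for Post-Treatment Week 4. The margin is 30 − 28 = 2 days, so a draw more than 2 days late would be dropped. A limit defined by visit avoids this.

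**The case against.** The strongest reply is that an on-treatment grade table is a coherent choice, that the data are reported elsewhere, and that the values that matter most clinically reach the adverse-event tables. Much of this stands. A reader might infer that Post-Treatment Week 4 labs are never reported; section 8.1.5 itself contradicts that. Investigators also assess the clinical significance of abnormal central results at that visit, and a value that needs treatment becomes an adverse event. The reply fails only for the untreated grade increase, which these routes need not count.

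The synopsis is not strong evidence of a contradiction. It is abbreviated, and the same paragraph also omits the 30-day limit that section 8.1.4 places on adverse events. It does leave two wordings of one output, which should agree.

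Two stronger readings should be resisted. First, a reader might infer that discontinuation labs are excluded, because section 5.4.1 allows that visit "no later than 2 days after their final dose of study drug". But the visit is ideally on the day of discontinuation, and it is a column of Table 5, titled "Study Activities – Treatment Period for Main study and Retreatment sub-study". Whether a lag of one or two days counts as on treatment is an ordinary windowing detail that can be left to the SAP. Second, a reader might take the one-in-four and one-in-five shares of draws as the share of affected subjects missed. That would require equal and independent risk at every draw, on and off drug. The protocol gives no such rates, and an abnormality that began on treatment and persists is already counted.

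**Conclusion.** The point holds in a narrow form. Section 8.1.5 leaves the required Post-Treatment Week 4 safety labs out of the only CTCAE-graded subject-level laboratory summary, and this matches neither the synopsis wording nor the adverse-event window in section 8.1.4. The loss is confined to grade increases that first appear at that visit and are not recorded as adverse events. Their number cannot be derived from the protocol. No data are lost and the primary efficacy analysis is unaffected. This is an inexpensive improvement to the reporting of a primary safety objective, not a flaw in the design. The conclusion assumes that the phrase about treatment in section 8.1.5 has the meaning given in the Definition of Terms, and it was reached from the protocol alone.

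**What to change.** In section 8.1.5, replace the words limiting the count to the treatment phase with: *from first dose through the PT Week 4 visit, including end-of-treatment and Premature D/C samples, and before any retreatment dose*. Show increases with on-treatment onset and post-treatment onset separately, so that the on-treatment count stays available. Apply the same rule to the Retreatment sub-study table, from the first retreatment dose. Naming the end-of-treatment and discontinuation samples also settles the one- or two-day question.

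The cost is one sentence and an added split in one table; the samples are already scheduled and processed centrally. The downside is small: some post-treatment grade changes will not be caused by study drug, and showing their onset separately lets the reader judge them.
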